## 6. ONGOING GRANTEE AND LOCAL EVALUATOR COORDINATION

*Describe how the grantee and local evaluator collaboratively worked together to identify the research question(s) and research design to ensure its feasibility and relevance. Describe how the grantee and local evaluator will continue to work together throughout the evaluation to proactively address unforeseen challenges as they arise and ensure the rigor and relevance of the evaluation and its findings. Describe how the grantee and local evaluator will coordinate dissemination efforts. Describe how these processes will occur while maintaining the independence of the evaluation.*

The basis for ongoing coordination between Action for Children (the grantee) and MER (the local evaluator) is regular communication, by way of recurring meetings and daily interactions with embedded staff. Throughout the original proposal process, and now during the evaluation planning phase, MER worked in consort with AFC to design a study with research questions that are appropriate to the intervention. MER guides the process, given our experience designing and running evaluations, and AFC provides expertise on their community, target population, and program/curricula specifics.

Recurring meetings will include a bi-weekly project CQI team meeting. Under the leadership of the Data Manager and Lead MER Evaluator, the CQI team reviews data from the nFORM and local evaluation systems to identify and mitigate implementation or data issues, and closely examine trends and accomplishments. This team includes AFC organizational and project leadership, the MER Evaluation team, and front-line staff representatives (e.g., Facilitators, Case Managers).

In addition to CQI team meetings, overall project team meetings occur monthly (at a minimum), with project leaders across MER and AFC in attendance, to ensure the partnership remains strong and that coordination across organizations is on track. This recurring, ongoing meeting structure is conducive to close coordination, ensuring that challenges can be quickly addressed, and promising strategies can be efficiently maximized.

One of the key components of this coordination effort is the Data Manager, who is an AFC employee. The Data Manager functions to bridge the gap between organizations. They will interact with AFC staff daily while completing their job duties and play a leadership role in the recurring meetings outlined above. See Section II.D. above for more details about this role and others. Both the meetings and the roles outlined above will continue throughout the entire project period, providing opportunities to ensure the rigor and relevance of the evaluation and its findings, and to discuss and coordinate dissemination efforts (which will also be shared across MER and AFC).

MER has experience operating prior descriptive evaluations using this exact process. Clearly outlining roles and responsibilities maintains the independence of the evaluation. That is, the evaluation team helps identify and illuminate areas of concern or improvement (for the program and the evaluation), but the program staff have responsibility for implementing improvements and providing direct services to participants. In this way, AFC and MER acknowledge our shared interest in and responsibility for a well-executed project and evaluation, but that MER is also an

independent and external organization with a high level of integrity and is not responsible for nor invested in the specific outcomes of the program. This allows for close coordination without allowing for co-dependence, or for personal interests to influence evaluation findings.

## 8. SAMPLE

### 8.1. TARGET POPULATION(S)

*For each target population identified in Section 1.2, please describe the target population(s), and explicitly state whether the population(s) differs from those who will be broadly served by the grant. Describe how the target population will be identified. Explicitly state the unit of analysis (e.g., non-residential father, unmarried couple).*

Description of Target Population	How is the population different from those who will be broadly served by the grant?	How will the target population be identified?	Unit of Analysis
18+ year old urban fathers in Franklin County (OH) with children age 24 and under	No difference: all program participants will be study participants	The sample will be identified and recruited by the program staff.	Urban adult fathers

### 8.2. POWER ANALYSIS

*For each confirmatory outcome, please provide power analyses demonstrating proposed sample sizes will be able to detect expected effect sizes for the outcomes targeted. Refer to previous studies of similar interventions for estimates of the required sample to inform power analyses. Note: If an impact evaluation is not proposed, this issue does not need to be addressed. You may use the table below to report the assumptions used in your power calculations, as well as the resulting minimum detectable impact for your confirmatory outcomes or provide them in the space below.*

Though not an RCT, the Power Analysis is as follows:

	Outcome 1:	Outcome 2:	Outcome 3:
Outcome Name	Parenting Attitudes	Father Relationship Behavior (parenting/co-parenting)	Father Financial Behavior
Continuous or binary?	Continuous	Continuous	Continuous

Level of significance (e.g., 0.05 percent)	0.05	0.05	0.05
Number of sides of test (one- or two-tailed)	2 tailed	2-tailed	2-tailed
Power (e.g., 80 percent)	80%	80%	80%
Total number of individuals in analytic sample	483	483	483
If continuous outcome, enter the standard deviation of the outcome (>0)	nFORM	nFORM	nFORM
Proportion of individual-level (or within-group) variance explained by covariates	nFORM	nFORM	nFORM
Minimum detectable effect size	0.030	0.030	0.030

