## 9. DATA COLLECTION

### 9.1. CONSTRUCTS AND MEASURES

*Clearly articulate the constructs of interest, measures to evaluate those constructs, and specific data collection instruments. Provide any information on the reliability and validity of the data collection instruments. For standardized instruments, you may provide the citation for the instrument.*

Construct	Measure	Instrument	Reliability and Validity (if standardized instrument, you provide a citation for the instrument)
Parenting Behavior (interaction with children)	1 item: hours spent w/children in last 30 days (interval); 1 item: frequency reach out to children (categories, 5-point scale); 7 items: frequency engage in key behaviors (categories, 5-point scale)	nFORM Community-Based Fathers Survey (A2b, A2c, A5b: b-d, f-i)  *also asked on OLLE; will use data from survey with the most complete data	n/a

Co-Parenting Behavior	11 items: frequency of agreement with key co-parenting behaviors (interval, 5-point scale)	nFORM Community-Based Fathers Survey (A13: a-k)  *also asked on OLLE; will use data from survey with the most complete data	n/a
Father Financial Behavior	2 items: yes or no questions for have resume, checking/savings accounts (dichotomous)	nFORM Community-Based Fathers Survey (B3, B3a)  *also asked on OLLE; will use data from survey with the most complete data	n/a
Parenting Attitudes (toward children)	7 items: frequency of key attitudes (categories, 5-point scale)	nFORM Community-Based Fathers Survey (A3: a-g)  *also asked on OLLE; will use data from survey with the most complete data	n/a

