All in Dads! Healthy Marriage and Responsible
Fatherhood Program Evaluation

Statistical Analysis Plan

NCT05194020

October 17, 2024

1. Data Analysis

Briefly describe the planned approach for data analysis. If an impact analysis is proposed, name the key dependent and independent variables, and describe any methods to minimize Type I error (i.e., finding positive impacts by chance) such as limiting the number of impacts to be analyzed and/or multiple comparison correction. Describe proposed approach(es) for addressing missing data.

Identify study sample

The study sample includes participants who: 1) gave recorded informed consent to be part of the study, and 2) took both an entrance and exit survey (for attitudinal outcomes) or entrance and follow-up survey (for behavioral outcomes). The CONSORT diagram in Figure 2 shows exclusion criteria and the anticipated size of the overall study sample. The analytic sample for particular outcome measures will vary based on missing data.

Defining analysis measures

For each outcome construct, we have identified the relevant measures from nFORM that are theoretically aligned with that construct. We will generate a correlation matrix between items in a given construct to ensure that theoretically related items are also empirically related in our data set. Items that are not strongly correlated with other items in a construct will be removed as necessary. Factor analysis will be used to ensure that all construct items hang together (using an alpha of 0.7 or higher as the threshold). If an alpha of 0.7 cannot be obtained, that outcome will be removed.

Once we are confident that all of the items align with a given construct, we will create a composite measure by taking an average of the scores on each non-missing item in the construct. The measure definition matrix below provides information on each proposed outcome. For composite measures, a change score will be calculated between a participant's pre-program composite score and post-program composite score. For standalone survey items, a change score will be calculated between a participant's pre-survey and post-survey responses.

For the sake of consistency and simplicity, parenting and co-parenting analyses will use a participant's youngest child as the focal child.

Model Specification to Predict Outcomes With Dosage

Construct by Outcome	Dependent Variables (follow-up)	Response Codes for Dependent Variables	Dependent Variable Type	Independent Variables

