Primary outcome:				
Parenting Behavior: 1 item	HOURSFU	# hours spent with child		Dosage: hours of attendance per service
	REACHFU	1 = Almost every day to 5 = never in past month	Continuous	

1 item 11 scaled items Co-parenting Behavior: 11 scaled items	ENGAGFU	1 = never to 5 = every day or almost every day	(using nFORM data); Co-variates: development starting points, risk - family structure, demographics, socioeconomic (ACS & OLLE survey data at baseline)
	COPARFU	1 = strongly disagree to 5 = strongly agree	
		1 = yes, 0 = no	

Secondary outcome:

Parenting Attitudes: 7 scaled items Financial Readiness 1 item 1 item	PATTFU	1 = always to 5 = never	Continuous	Dosage: hours of attendance per service (using nFORM data); Co-variates: development starting points, risk - family structure, demographics, socioeconomic (ACS & OLLE survey data at baseline)
	SAVFU			
	CHECKFU	1 = yes, 0 = no	Dichotomous	

Handling missing data

Outcomes

When creating the composite measures for co-parenting and parenting relationships, we will create a composite score by taking the average of multiple individual items. For these measures, our current plan is to use 20% as a threshold for allowable missing items, based on guidance from evaluation technical assistance resources. This plan is contingent on the final distribution of missing data in our data set. With a 20% threshold, if a respondent is missing more than 1 item used for creating the co-parenting construct or more than 2 items for creating the parenting construct, the respondent will be assigned a missing value for that construct. We will not be imputing truly missing values for outcomes. To create a construct score, the average will divide by the number of non-missing values in the construct.

Participants who have not seen their child within the past month will have their parenting behavior responses set to "Never" (1) and will be included in the analytic sample for that outcome.

For outcomes that use single survey items, participants who do not respond to the item on either the pre- or post-survey will be excluded from the analytic sample for that outcome.

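### The confirmatory parenting question R1 has no fixed endpoint: hours, reach-out and engagement are listed with no deciding rule, and reach-out is coded in the opposite direction with no reversal stated

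*Protocol*

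**What the plan says.** Protocol 1.1 and 1.2 make R1 (parenting behavior) a primary, confirmatory question, separate from R2 (co-parenting). Its endpoint is then described in several places.

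- **Protocol 8.2** has no R1 column. One column, headed "Father Relationship Behavior (parenting/co-parenting", covers R1 and R2 together.
- **Protocol 9.1** defines one parenting-behavior construct: "1 item: hours spent w/children in last 30 days (interval); 1 item: frequency reach out to children (categories, 5-point scale", plus seven engagement items on a 5-point scale.
- **SAP section 1, Defining analysis measures**, says of each construct that "we will create a composite measure by taking an average of the scores on each non-missing item in the construct". The same subsection gives standalone survey items their own change score. It also allows poorly correlated items to be removed, and a whole outcome to be removed if alpha does not reach 0.7.
- **SAP section 1, model specification table**, lists HOURSFU (a count of hours), REACHFU and ENGAGFU as separate dependent variables. REACHFU is coded "1 = Almost every day to 5 = never in past month"; ENGAGFU is coded "1 = never to 5 = every day or almost every day". COPARFU, for R2, is a further separate variable.
- **SAP section 1, Handling missing data**, recodes the parenting-behavior responses of fathers who have not seen their child in the past month to 1, labelled as never.
- **SAP section 1, Analytic approach**, plans a paired t-test per outcome and promises p-values adjusted for multiple testing, reported in an appendix. It names no method and no family of tests.

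Neither document mentions reverse scoring or standardizing, or says which result decides R1.

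**The concern.** A confirmatory question needs one result, or a stated rule over several results, that answers it. Two readings of R1 are open: a construct average that includes hours and reach-out, or three separately tested variables.

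On the first reading, a count of hours is averaged with 5-point codes, and one of those codes runs backwards. On the second, one variable can improve significantly while the others do not, and nobody can say from the plan whether R1 was confirmed.

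The direction of REACHFU matters beyond averaging. The correlation and alpha screens operate on the scores as coded, and the recoding to 1 means opposite things on the two frequency scales.

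**Working it through.** **Inputs from the documents.** Seven engagement items, one reach-out item and one hours item (Protocol 9.1). Codings (SAP table). Equal-weight mean of non-missing items and an alpha threshold of 0.7 (SAP, Defining analysis measures). Recoding to 1 (SAP, Handling missing data). N = 483, two-sided 0.05, power 80%, minimum detectable effect 0.030 (Protocol 8.2).

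**Assumptions.** The documents give no SDs or correlations. I take an hours SD of 50 to 200, an item SD of 1.0 to 1.2, an inter-item correlation of 0.4 to 0.5, and hours uncorrelated with the other items.

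**1. The plan's own figure.** For a paired t-test, the detectable standardized change is (1.960 + 0.842)/√483 = 0.127, not 0.030. Section 8.2 does not state the metric of 0.030. That discrepancy is a separate matter and nothing below rests on it. It means only that the figure cannot show which variable the shared column was computed for.

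**2. Literal nine-item average.** Item SD 1.2, correlation 0.4.
- Variance from hours at SD 100: (100/9)² = 123.46.
- Variance from the eight other items: 8 × 1.2² × (1 + 7 × 0.4)/81 = 43.776/81 = 0.540.
- Share due to hours: 123.46/124.00 = 99.6%. At SD 200 it is 99.9%.
- At SD 50, with item SD 1 and correlation 0.5: 30.86/(30.86 + 0.44) = 98.6%.

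**3. Reach-out averaged unreversed with the seven engagement items.** If all eight behaviors improve by 0.30, the REACHFU code falls by 0.30. The mean change is (7 × 0.30 − 0.30)/8 = 0.225, which is 25% too small.

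**4. The alpha screen on the same eight items.** Equal SDs, correlation 0.4.
- Scored in one direction: (8/7) × (1 − 8/30.4) = 0.84.
- REACHFU unreversed: (8/7) × (1 − 8/19.2) = 0.67, below the SAP's 0.7.

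**5. The recoding rule.** Take a father with REACHFU 3 at entry who has not seen his child in the month before follow-up. Recoding gives 3 → 1, which reads as a two-point improvement, because 1 is the most frequent category. The least frequent category would be 5, a two-point worsening. Reversing afterwards does not help: 6 − 1 = 5, still the best score. The order of the two steps must therefore be stated.

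**6. Three separate tests.** Suppose each variable truly changes enough for 80% power at 0.05. If they are independent, the chance that some but not all are significantly favorable is 1 − 0.8³ − 0.2³ = 0.48. Simulation (400,000 draws) gives 40% at correlation 0.3 and 30% at 0.6. In those cases the plan gives no answer to R1.

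**The case against.** **Hours and reach-out are probably meant to be standalone.** The SAP separates composites from standalone items, gives single-item outcomes their own missing-data rule, and gives the three variables their own names. The other single items are binary and reported as percentages, so the standalone change-score rule fits hours and reach-out naturally. I accept that this is the more plausible intent. A reader might infer from steps 2 and 3 that the SAP clearly plans a nine-item average; it does not. But neither document says the two items stay out of the composite, and Protocol 9.1 puts them in the construct. The missing-item limit does not settle membership either: 20% of 7 or 9 items is 1.4 or 1.8, yet the SAP allows two missing parenting items.

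**The screen would expose a reversed item.** Probably, so silent attenuation is less likely than step 3 alone suggests. Raw alpha for the nine-item average at hours SD 100 would be about (9/8) × (1 − 10,011.5/10,043.8) = 0.004, so that composite would be flagged too. But the SAP's remedy is to remove the item or the outcome, not to correct its direction. A coding artifact could then remove part or all of a primary outcome.

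**Opposite coding is harmless if REACHFU is tested alone.** True, since its codes are printed beside it. The exception is the recoding rule. The label never with code 1 matches only ENGAGFU, so the rule was probably written for that scale, but as worded it covers all parenting-behavior responses.

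**Multiplicity is handled.** A reader might infer that R1 carries a false-positive risk of about 14%, from 1 − 0.95³ = 0.143. That is not a property of this plan: adjusted p-values are promised, and in the favorable direction the unadjusted figure is 1 − 0.975³ = 7.3% for independent tests. Adjustment still does not say which variable answers R1.

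**The power column may record shared assumptions.** This stands. A reader might infer a pooled parenting and co-parenting analysis from the label. No analysis computes one, and COPARFU is listed separately. The template also makes power analysis optional for a descriptive study.

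**Conclusion.** The point holds, and should be corrected because R1 is primary and confirmatory. The documents leave open whether hours and reach-out belong to the parenting composite, do not state a direction for REACHFU, and do not say which result decides R1.

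The size depends on the reading. Under a literal average, hours supplies about 99% or more of the variance. With reach-out alone added unreversed, a 0.30 improvement shows as 0.225, and alpha falls from 0.84 to 0.67. Under separate tests, a split result would occur in roughly 30% to 48% of studies if each test had 80% power. These figures rest on assumed SDs and correlations. The recoding problem needs no such assumption, only that REACHFU counts as a parenting-behavior response, which is where the SAP table lists it.

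The documents do not support going further: the power table's label is not evidence of a pooled analysis, and no particular one of the three variables is shown to be the only correct endpoint.

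**What to change.** In the SAP:

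1. State that HOURSFU and REACHFU are standalone and are never averaged into the engagement composite, and list the items in ENGAGFU. Protocol 9.1 gives seven; the SAP table appears to give eleven, but it is broken in the text available and needs checking.
2. Reverse-score REACHFU (6 − x) before any correlation, alpha or change score. State the direction of PATTFU at the same point, so that a positive change always means healthier.
3. Limit the recoding to 1 to ENGAGFU, or apply it after REACHFU is reversed. The first option keeps reach-out answers that fathers actually gave.
4. Name one deciding R1 endpoint, for example the ENGAGFU mean with the other two supportive, or a ranked set with a stated multiplicity rule.

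In Protocol 8.2, tie the power statement to the named R1 and R2 variables separately. Splitting the column alone would only repeat the same entries.

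**Cost.** Wording only; the variables not chosen become supportive. If all three are kept as co-deciding with a Bonferroni split, the detectable change at N = 483 rises from 0.127 to (2.394 + 0.842)/√483 = 0.147 SD of change. The SAP is dated October 17, 2024, and the protocol schedules follow-up to May 31, 2025 at the latest. The choice should be recorded before follow-up scores are analyzed, or labelled as made afterwards if they already have been.

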Missing data for the implementation outcomes could happen as a result of programmatic data entry issues. For the sake of this evaluation, we assume that any primary or support services received by a participant are being accurately logged into nFORM, so a lack of documented attendance, service contacts, referrals, etc. is indicative of lack of services (i.e., a participant not receiving the program components as intended).

Assessing non-response bias

We will conduct response rate analysis for each primary outcome of interest to assess non-response bias and adjust for threats to internal validity. Using data from the Applicant Characteristics Survey, we will look at demographics (race, ethnicity, age, education level) and primary reason for joining the program among participants who fall into each of the following categories: 1) non-respondents who answered no surveys after the ACS, 2) respondents who completed the pre-survey only, 3) respondents who completed the post-survey only, and 4) respondents who completed both the pre- and post-survey (complete case).

Analytic approach

The main goal of this descriptive study is to assess pre-post change scores in the attitudinal outcomes listed above and assess pre-to-one-year follow-up change scores in the behavioral outcomes listed above among program participants before and after primary workshops. We will use paired sample t-tests to assess the magnitude and significance of changes among program participants in the analytic sample for each outcome. For binary economic stability outcomes, we will descriptively report the percent of participants who opened a checking or savings account one year after enrollment, compared to the percent who had opened these accounts before the program. We will adjust our p-values for multiple hypothesis testing and report the adjusted p-values in the appendix of the final report.

2. Data Archiving and Transfer

Briefly describe the planned approach data arching and transfer by addressing questions below.

What procedures and parameters are established for all aspects of data/information collection necessary to support archiving data collected as part of the evaluation?

Examples include informed consent, data maintenance, de-identifying data procedures.

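### Protocol 8.2 gives a continuous-outcome power figure for Father Financial Behavior (R3), but R3 is measured by yes/no items that the SAP only describes, so the figure matches no planned analysis

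*Protocol*

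**What the plan says.** Protocol 8.2 has one column per outcome. Under "Continuous or binary" all three columns, including Father Financial Behavior, read Continuous. The financial column then gives a two-tailed 0.05 level, 80% power, 483 under "Total number of individuals in analytic sample", and a minimum detectable effect size of 0.030. The row "If continuous outcome, enter the standard deviation of the outcome (>0" holds only the word nFORM, with no number.

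Protocol 9.1 defines the same construct as "2 items: yes or no questions for have resume, checking/savings accounts (dichotomous", and 9.3 repeats this. The SAP outcome table lists SAVFU and CHECKFU as two one-item variables, coded 1 for yes and 0 for no and typed Dichotomous. The SAP's Analytic approach paragraph says: "For binary economic stability outcomes, we will descriptively report the percent of participants who opened a checking or savings account". It names no test for them.

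Protocol 1.1 makes R3 a secondary outcome and asks whether the improvement is significant. Protocol 1.2 labels R3 confirmatory.

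**The concern.** The power table describes one kind of outcome, and the measurement sections and the SAP describe another. A reader of 8.2 would conclude that a confirmatory question has a sized test behind it. In the SAP, the one-year change in these items is a pair of percentages.

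The type of outcome also decides which inputs a calculation needs. For a yes/no item measured twice on the same father, the detectable net change depends on the share of fathers who switch in either direction. The table gives neither that share nor a numerical SD, so the R3 column cannot be checked from what is written.

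**Working it through.** **Inputs.** From Protocol 8.2: n = 483, two-sided 0.05 (z = 1.96), 80% power (z = 0.8416), stated detectable effect 0.030. From the SAP: paired comparison of baseline with one-year follow-up. Not in the documents: the SD, the baseline proportions, the pre-post correlation and the share of fathers who switch.

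**1. Reproduce 0.030 as a paired continuous outcome.**
- Detectable effect in SDs of the change score = (1.96 + 0.8416)/√483 = 2.8016/21.98 = 0.127.
- In SDs of the raw score, multiply by √(2(1 − ρ)): 0.180 at ρ = 0, 0.127 at ρ = 0.5, 0.057 at ρ = 0.9. Reaching 0.030 needs ρ of about 0.972.
- Power for 0.030 SD of change at n = 483 is about 10%. For 80% power, n = (2.8016/0.030)² ≈ 8,721 pairs.
- If 0.030 is read as a regression f², power at n = 483 is 97% with one tested predictor, 85% with five and 77% with eight. The documents specify neither that reading nor a number of predictors.

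The stated figure therefore does not reproduce. The three columns carry identical entries, so this applies equally to all of them.

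**2. The same n for a paired yes/no item (McNemar, normal approximation).** Let p be the share who switch status and d the net change. Solve

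n = (1.96√p + 0.8416√(p − d²))² / d² for d at n = 483:

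| Assumed share switching | Detectable net change |
|---|---|
| 10% | 4.0 points |
| 20% | 5.7 points |
| 30% | 7.0 points |

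Over a wider assumed range the result runs from 2.8 points (5% switching) to 9.0 points (50%).

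**3. Compare the two scales.** Multiplying 0.1275 by √0.10, √0.20 and √0.30 gives 0.040, 0.057 and 0.070, the same values as in step 2. The paired continuous formula and McNemar nearly coincide here, because the SD of a 0/1 change is close to √p.

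**4. Which analysis could the 8.2 entry describe?**
- *A continuous financial score:* none is defined. The SAP's missing-data text describes composites for parenting and co-parenting only.
- *The one-year comparison:* descriptive percentages, with no test.
- *The dosage model table:* it lists the two items as dichotomous dependent variables and names no method. The 8.2 entries do not describe such a model.

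**The case against.** **The table was optional.** The template in 8.2 says power need not be addressed without an impact evaluation. Study enrolment ended in spring 2024 (3/31/2024 in Protocol section 3, 4/12/2024 in 8.3), before the SAP date of October 17, 2024. This stands: a correction cannot change the sample size, and R3 is secondary. But the plan chose to give a figure for an outcome it calls confirmatory, and the figure should describe that outcome.

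**The SAP's t-test sentence could cover these items.** It refers to paired t-tests for each outcome, and change scores are planned for standalone items. The next sentence, however, sets the binary items apart as descriptive. Even if the t-test did apply, step 1 shows that 0.030 would not follow.

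**Stronger readings that the documents do not support:**
- *A standardised effect cannot be defined on 0/1 data, or SD units could never repair the entry.* Step 3 shows otherwise. The label alone moves the number very little; the shortfall comes mainly from the 0.030 common to all columns.
- *R3 has only 55%, 31% or 22% power at 10%, 20% or 30% switching.* These values follow if 0.030 means 3 percentage points (80% then needs about 5.6% switching or less). The table calls 0.030 an effect size and does not offer that reading.
- *Only 70% of 483, or 338 fathers, will be analysed.* Protocol 9.5 does expect 70% response at one year. But 8.2 labels 483 the analytic sample, and the SAP defines the behavioural sample as those with both surveys. Taking 70% again would apply attrition twice. The flow diagram that might settle this is not readable in the text reviewed.
- *80% is an achieved power.* It is an input to a detectable-effect calculation.

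**Conclusion.** The concern holds as an inconsistency between Protocol 8.2 and Protocol 9.1, 9.3 and the SAP. The R3 column gives a continuous-outcome power statement for separate yes/no items that the SAP will report descriptively, so it corresponds to no planned analysis. The contradiction itself needs no assumption.

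The size has two parts. As a paired continuous outcome, 483 people detect about 0.127 SD of change, roughly four times the stated 0.030 (0.127/0.030 = 4.2). That belongs to the whole table and should not be counted again against R3. Specific to R3 is the translation into percentage points: about 4.0 to 7.0 points for 10% to 30% switching. Those shares are assumptions, and the result takes 483 as the number with both surveys.

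This should be corrected, but it does not threaten the conduct of the study or the descriptive reporting of these items.

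**What to change.** 1. **Reconcile the items first.** Protocol 9.1 and 9.3 list a resume item and a checking/savings item. The SAP lists what appear to be separate savings and checking items. State which items make up R3.
2. **Correct 8.2.** Mark Outcome 3 as Binary, and remove its SD entry and the 0.030 with 80% power.
3. **Choose one route.** Either (a) name a paired binary test (McNemar) in the SAP for each item, include it in the multiplicity adjustment, and state in 8.2 the detectable percentage-point change over a stated switching range, for example 10% to 30%. Or (b) state no power for R3, relabel it as descriptive in Protocol 1.2, and remove the reference to significance in 1.1. If (a), date the change and make it before the follow-up data are analysed.
4. **Confirm what 483 counts.** Figures based on 338 belong in the plan only if the sponsor confirms that 483 is the enrolled number.

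The cost is a table edit and a few sentences. Data collection is unaffected. Route (a) replaces the present figure with a less favourable one; route (b) gives up the confirmatory label for R3.
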